4.7.6.2 CCI

For the CCI the following weights will be calculated:

- CCI
- CCI
- CCI
- CCI

Each domain score will be calculated as follows:

- CCI

The total score will be calculated as follows:

- CCI

Missing data will be dealt with as described in CCI CCI

Weights of each item and other details for calculation are reported in CCI CCI

The CCI and CCI CCI) assessed at Visits 3 - 7 (End of Treatment) will be summarised by treatment group using descriptive statistics including 25th and 75th percentiles. Results for absolute changes from baseline will also be reported. Due to CTP amendments and to the corresponding changes in the procedures schedule, not all the subjects have undergone the same sequence of assessments. All the values collected will be summarised jointly. Considering the presence of a stratified and permuted blocks randomisation list no imbalance between treatments is expected.

Change from baseline in CCI total score at Visit 3, Visit 4, Visit 5, Visit 6 and Visit 7 will be analysed using a linear mixed model for repeated measures including treatment, visit, treatment-by-visit interaction, use of stable concomitant therapy with oral macrolides and pooled site, i.e. country, as detailed in Section 4.9.1, as fixed effects and baseline value as covariate. An unstructured covariance matrix will be assumed and the Kenward-Roger adjustment will be used for the degrees of freedom. The least square means in each treatment group, the least square mean differences between treatments, their 95% CIs and associated p-values overall and at each visit will be estimated by the model. The OBSMARGINS option will be used. A two-sided p-value of <0.05 for the overall mean difference between treatments will be considered statistically significant.

The above summaries/analyses will be performed using the mITT and PP Populations. Results for the PP Population will be considered as supportive.

CONFIDENTIAL

Sponsor:	Zambon S.p.A.	Protocol Number:	Z7224L01
----------	---------------	------------------	----------

Notes:

- While for Visit 2, Visit 4, Visit 5, Visit 6 and Visit 7 the 3-month version of the CCI is used, for Visit 2 data are collected for the 4-week version. Visit 2 scores will not be included in the linear mixed model analysis but they will be included in the descriptive analysis.

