Change from baseline in each CCI [REDACTED] domain score will be analysed using a linear mixed model for repeated measures including treatment, visit, treatment-by-visit interaction, use of stable concomitant therapy with oral macrolides and pooled site, i.e. country, as detailed in CCI [REDACTED] [REDACTED], as fixed effects and baseline value as covariate. An unstructured covariance matrix will be assumed and the Kenward-Roger adjustment will be used for the degrees of freedom. The least square means in each treatment group, the least square mean differences between treatments, their 95% CIs and associated p-values overall and at each visit will be estimated by the model. The OBSMARGINS option will be used. A two-sided p-value of <0.05 for the overall mean difference between treatments will be considered statistically significant.

The above summaries/analyses will be performed using the mITT Population.

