- EoT should be replaced by the last time (in days) to event >270 days (if any);

- **Tables that require Cox proportional hazards model and 95% CIs of hazard ratios between treatments:**

*PROC PHREG data=dset;
CLASS treatment psite med;
MODEL time*event(1) = treatment psite med / ties=exact;
HAZARDRATIO 'Col. Sodium vs Placebo' treatment / cl=both;
BY byvar; (optional)
WHERE wherever; (optional)
RUN;*

Notes:

- Psite represents the pooled site, i.e. country, as detailed in [Section 4.9.1](#);
- Med represents use of stable concomitant therapy with oral macrolides (e.g. azithromycin or erythromycin or clarithromycin) (Yes/No);
- Time represents the time to event or time to censoring;
- Event represents the censoring indicator (1 = censored);
- If the option ties=exact requires a considerable amount of computer resources, the Efron approximation will be used (*ties=efron*).
- Treatment order: 1= Colistimethate Sodium, 2= Placebo.

CONFIDENTIAL

Sponsor:	Zambon S.p.A.	Protocol Number:	Z7224L01
----------	---------------	------------------	----------

- **Tables that require negative binomial modelling, including 95% CIs of treatment ratios:**

```
PROC GENMOD data = dset;
  CLASS treatment psite med;
  MODEL count = treatment psite med / offset=log_years link=log dist=negbin wald
  type3;
  ESTIMATE 'Col. Sodium / Placebo' treatment 1 -1 / exp;
  lsmeans treatment / ilink cl diff exp om;
  BY byvar; (optional)
  WHERE wherever; (optional)
RUN;
```

Notes:

- Psite represents the pooled site, i.e. country, as detailed in [Section 4.9.1](#);
- Med represents use of stable concomitant therapy with oral macrolides (e.g. azithromycin or erythromycin or clarithromycin) (Yes/No);
- Count represents the total number of exacerbations for each patient;
- log_years represents the logarithm of the follow-up time in years;
- Treatment order: 1= Colistimethate Sodium, 2= Placebo.

- **Tables that require linear mixed model for repeated measures and 95% CIs of differences between treatments:**

```
PROC MIXED data = dset;
  CLASS treatment visit psite med sub;
  MODEL change = treatment visit treatment*visit psite med baseline/ s ddfm=kr;
  REPEATED visit / subject=sub type=un r;
  LSMEANS treatment treatment*visit / om at means cl slice=visit;
  LSMESTIMATE treatment
  'Col. Sodium / Placebo' 1 -1 / cl;
  LSMESTIMATE treatment*visit
  'Col. Sodium / Placebo: Visit 4' 1 0 0 0 -1 0 0 0,
  'Col. Sodium / Placebo: Visit 5' 0 1 0 0 0 -1 0 0,

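### The questionnaire text and the mixed-model code do not agree on how visits are weighted in the deciding overall treatment difference

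*SAP*

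**What the plan says.** SAP 4.7.6.2 analyses change from baseline in the "total score at Visit 3, Visit 4, Visit 5, Visit 6 and Visit 7 will be analysed using a linear mixed model" for repeated measures, with treatment, visit and their interaction among the fixed effects. It then says that "the least square mean differences between treatments, their 95% CIs and associated p-values overall and at each visit will be estimated by the model". Directly after that comes the sentence on weighting and significance: "The OBSMARGINS option will be used. A two-sided p-value of <0.05 for the overall mean difference between treatments will be considered statistically significant". Section 4.7.6.9 applies the same model, weighting sentence and decision rule to each domain score.

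The PROC MIXED code in 4.14 has three relevant parts:

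- the model: "MODEL change = treatment visit treatment*visit psite med baseline/ s ddfm=kr";
- the statement that prints the means: "LSMEANS treatment treatment*visit / om at means cl slice=visit", which has the observed-margins option but requests no difference;
- the overall contrast, under `LSMESTIMATE treatment`: "Col. Sodium / Placebo' 1 -1 / cl", which has no observed-margins option.

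The visit contrasts that follow start at Visit 4 and have four coefficients per arm: "Col. Sodium / Placebo: Visit 4' 1 0 0 0 -1 0 0 0".

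Under 4.7.5 a secondary test can be significant only if every earlier test in the hierarchy is. Under 4.7.6.9 the domain scores are themselves tested in order.

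**The concern.** With treatment-by-visit in the model there is no single treatment effect. The overall difference is an average of visit-specific differences, so its value depends on the visit weights. The weighting sentence in 4.7.6.2 has no stated limit and follows one that covers means, differences and p-values, so it can be read as applying observed-margin weights to the tested difference. The code can be followed only as an equally weighted test.

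Two things are at stake. The significance rule in a fixed sequence should rest on one defined quantity. And a table whose overall arm means use one set of visit weights, while the difference and p-value use another, may not add up.

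Unequal visit counts are to be expected. SAP 3.9 plans for about 20% dropout, and 4.7.6.2 says that protocol amendments left subjects with different assessment sequences.

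**Working it through.** The SAP gives no numerical figure for this test, so there is none to reproduce.

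**Text against code.** That `LSMESTIMATE` does not inherit the observed-margins option from `LSMEANS`, and weights visits equally by default, is a premise about the software. The documents do not state it. Country, macrolide use and baseline have no interaction with treatment, so they cancel from every difference. Visit does not cancel from the overall difference. The contrasts at each visit are unaffected.

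The other models in 4.14 do not have this problem. The ANCOVA code requests difference and observed margins in one statement. The negative binomial code has a separate contrast, but no treatment interaction.

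**Inputs from the SAP (3.9).** 377 randomised, about 188 per arm; dropout about 20%.

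**Assumptions.** Linear monotone dropout; SD 15; within-subject correlation 0.6 × 0.9^(gap in months/3); visit margins pooled over arms; no dataset rows for missed visits; the effect profiles shown.

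**Formulas.** Retention at month m is a = 1 − 0.20 × m/12. The equal-weighted estimate is the simple mean of the visit differences d. The observed-margin estimate is Σ(a·d)/Σa.

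**Visits 4 to 7 (months 3, 6, 9, 12).** Retention is 0.95, 0.90, 0.85, 0.80, which sums to 3.50. The weights are 0.271, 0.257, 0.243, 0.229, against 0.25 each. The standard errors from the repeated-measures covariance are 1.282 (equal) and 1.281 (observed margins). With the effect scaled so that the equal-weighted z is 1.96, the other z is 1.96 × (ratio of estimates) × (1.282/1.281).

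| Visit differences | Equal | Observed margins | Gap | Equal p = 0.050 becomes |
|---|---|---|---|---|
| −4, −4, −4, −4 | −4.00 | −4.00 | 0 | 0.0497 |
| −2, −3, −4, −5 | −3.50 | −3.43 | 0.07 (2.0%) | 0.055 |
| −6, −4, −2, 0 | −3.00 | −3.14 | 0.14 (4.8%) | 0.040 |

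For the third row: (0.95×6 + 0.90×4 + 0.85×2 + 0.80×0)/3.50 = 11.0/3.50 = 3.14.

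At 50% power the two significance decisions disagree in 1.0%, 1.7% and 3.8% of simulated trials for the three rows. The two estimates correlate at 0.9995.

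**Sensitivity.**

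- Visits 4 to 7, the two varying profiles: p becomes 0.045 to 0.052 with 10% dropout and 0.034 to 0.057 with 30%.
- Five visits (3 to 7), 20% dropout, effects −1 to −5: −2.90 against −3.00 (3.5%), and p becomes 0.058.
- Five visits, 20% dropout, only 30% of subjects with a Visit 3 form, effects 0, −1, −3, −5, −6: −3.35 against −3.00, and p becomes 0.026. The documents do not give the share with a Visit 3 form.
- Over all scenarios tried, the decisions disagree in 0.5% to 12% of trials at 50% power.

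**The case against.** The strongest reply is that text and code can be reconciled. Sections 4.7.6.3 and 4.7.6.6 restrict observed margins to the least-squares means. If that limit is read into 4.7.6.2 and 4.7.6.9, the option governs the arm means and the test comes from the separate contrast. Section 4.14 describes only the descriptive and frequency code as examples, so the mixed-model code reads as specification. On this reading the deciding p-value is already equal-weighted, and the fix changes no significance decision.

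Much of this stands. It is a fair reading, and it reduces the point to a clarification of wording plus a display mismatch. But the limiting phrase is missing from the two sections where it matters, and nothing says whether text or code governs. Even on this reading, the overall arm means and the tested difference use different visit weights.

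The reply is also right that the consequence is limited. A gap needs both unequal visit counts and an effect that varies by visit. If missed visits do have rows in the analysis dataset, which the SAP does not define, the two weightings would nearly coincide.

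**Conclusion.** The mismatch is real and should be corrected, but its effect is modest. For Visits 4 to 7 with about 20% dropout, the overall estimates differ by about 0 to 5%: at most 0.14 points, against a standard error of about 1.28, in the profiles tried. Only a result close to 0.05 could change side. Very uneven Visit 3 completion could widen the gap. SD, correlation, dropout pattern and effect profiles are assumptions.

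Three stronger readings are tempting, and the documents do not support them:

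- **The printed means never subtract to the printed difference.** For a constant effect the two weightings estimate the same quantity; what remains is sampling noise, with SD about √(1.282² + 1.281² − 2 × 0.99949 × 1.282 × 1.281) ≈ 0.04 points in the Visits 4 to 7 case.
- **The gatekeeping p-value cannot be determined.** Following the code gives one definite answer.
- **The ambiguity is known to open or close an important gate.** A gating role follows from 4.7.5, but the order of the endpoints there is redacted, so neither the rank of the total score nor what lies behind it can be seen.

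**What to change.** 1. Reconcile the visit set first. The text models Visits 3 to 7; the code's visit contrasts cover Visits 4 to 7. The note closing 4.7.6.2 also needs correcting, because it assigns Visit 2 to both recall versions of the questionnaire.
2. State in 4.7.6.2 and 4.7.6.9 that the overall effect is the equally weighted average of the modelled visits, and that observed margins apply only to country and macrolide use.
3. Take arm means and difference from one specification, with coefficients and divisor that match the visit set. For five visits: `LSMESTIMATE treatment*visit 'overall' 1 1 1 1 1 -1 -1 -1 -1 -1 / divisor=5 om cl`. For four visits: four coefficients per arm and `divisor=4`. Add matching single-arm rows for the two means. Four-visit coefficients must not be used with a five-visit model, because the coefficients would fall on the wrong cells.
4. SAP Addendum 2.2 records that the database is locked and the study unblinded. State in the trial report which weighting and visit set produced the reported p-values, and whether missed visits had rows in the dataset. Show the other weighting as a check, and label any change post hoc, as the SAP Introduction requires.

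The weighting costs one sentence in each section and a few lines of code, and no new data.

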4.7.6.3 CCI

Summary statistics of the CCI and absolute change from baseline will be provided by treatment group for each trial visit.

Due to CTP amendments and to the corresponding changes in the procedures schedule and due to differences in the schedule of assessments in the local versions of the CTP, not all the subjects have undergone the same sequence of laboratory assessments. All the values collected will be summarised jointly. Considering the presence of a stratified and permuted blocks randomisation list no imbalance between treatments is expected.

The CCI as determined by CCI (Visit 2) to Day 28 (Visit 3) will be compared between the treatment groups by an ANCOVA model including treatment, pooled site, i.e. country, as detailed in Section 4.9.1, and use of stable concomitant therapy with oral macrolides as fixed effects and baseline value as covariate. Least square means in each treatment group, least square mean difference between treatments, their 95% CIs and associated p-value will be estimated. OBSMARGINS option will be used for least square means estimates. A two-sided p-value of <0.05 for the overall mean difference between treatments will be considered statistically significant.

The analysis of covariance model will include only complete cases. CCI analysis might be added during the blind review meeting.

The above summaries/analyses will be performed using the mITT Population.

4.7.6.4 CCI

A single endpoint of the number and the percentage of subjects with severe CCI will be presented. CCI documented on the CCI form of the eCRF are presumed to include episodes of pneumonia which require intravenous antibiotics and/or hospitalisation. CCI form of the eCRF that is linked to an adverse event with a Preferred Term of 'Pneumonia' but does not have any associated intravenous antibiotics or hospitalisation will be assumed to be a CCI. Data will be reviewed during the blind review meeting and documented in the Blind Data Review and Analysis Sets Report.

A CCI will be defined as treated with systemic antibiotic therapy if a treatment is recorded in the Systemic Antibiotic Therapy form of the eCRF.

The corresponding adjusted mean annual CCI rate estimated by a negative binomial model with the same characteristics as the primary efficacy model as detailed in Section 4.7.4 will be analysed. The adjusted mean annual CCI in each treatment group and the adjusted rate ratio with their 95% CIs will

CONFIDENTIAL

Sponsor:	Zambon S.p.A.	Protocol Number:	Z7224L01
----------	---------------	------------------	----------

be estimated by the model. An adjusted rate ratio <1 will indicate that colistimethate sodium decreases the rate of CCI compared to placebo. A two-sided Wald chi-square test p-value of <0.05 will be considered statistically significant. P-values of the effects based on Wald chi-square test will also be presented.

The above summary/analysis will be performed using the mITT Population.

4.7.6.5 CCI

The time to first severe NCFB pulmonary exacerbation will be analysed and tested using a log-rank test as detailed in Section 4.7.6.1 for the CCI.

A log-rank sum test will be used to compare the survival distributions of the two treatment groups. A two-sided p-value of <0.05 will be considered statistically significant.

The above summary/analysis will be performed using the mITT Population.

4.7.6.6 CCI

The CCI will be presented by treatment group.

It will be computed with the following formula:

$$\text{CCI} = \frac{(\text{follow-up time [days]} - \text{sum of durations of CCI})}{\text{follow-up time (years)}}$$

Follow-up time will be computed as detailed in Section 4.1.7.

For CCI with a resolution date after the treatment completion/discontinuation, the number of days of duration after the treatment completion/discontinuation, i.e. out of the follow-up period, will be subtracted from the sum of durations of CCI.

Non-parametric ANCOVA model with a randomisation-based methodology as proposed by Koch et al [4] will be used to analyse the ratio of the means between colistimethate sodium and placebo adjusting for any covariates effect and test the null hypothesis of the ratio of means equal to 1. Considering the sample size foreseen for this analysis, there won't be any correction for type I error. A LOGRATIO conversion will be applied.

The model will include treatment group, pooled site, i.e. country, as detailed in Section 4.9.1, and use of stable concomitant therapy with oral macrolides as covariates. No stratification variable will be included.

Treatment effect coefficient will be presented along with standard error, associated test statistic and two-sided p-value. A two-sided p-value of <0.05 will be considered statistically significant.

Treatment effect coefficient and associated 95% CI will be exponentiated to obtain estimates and 95% CI for the ratio of the means.

Due to the fact that the p-value computation is based on the re-randomisation of the population, while the CI is based on repeated random sampling theory, there might be disagreement regarding the treatment effect using these two different approaches. Even if these occurrences are quite infrequent, it's worth stating that the p-value from the randomisation test is based on a more realistic and minimal assumptions and should take precedence [5].

CONFIDENTIAL

Sponsor:	Zambon S.p.A.	Protocol Number:	Z7224L01
----------	---------------	------------------	----------

As a supportive analysis, the annualised number of [CCI] days will also be compared between the treatment groups using an ANCOVA model including treatment, pooled site, i.e. country, as detailed in Section 4.9.1, and use of stable concomitant therapy with oral macrolides as fixed effects. Least square means in each treatment group, least square mean difference between treatments, their 95% CIs and associated p-value will be estimated. OBSMARGINS option will be used for least square means estimates.

4.7.6.7 [CCI]

Total number of [CCI] and [CCI] will be described overall and by treatment group.

Total number of [CCI] per patient will be computed by summing [CCI] form. Number of [CCI] will be computed considering [CCI]. Namely:

- [CCI]

Where:

- $\frac{[CCI]}{[CCI]} = \text{sum} \{ [CCI] 1, [CCI] 2, \text{etc.} \} / [CCI]$
- $[CCI] \text{ Assessment } i = \text{Coeff } i * \{ (part1) [(Date of Assessment i) - (Date of Assessment i-1) + 1]/2 + (part2) [(Date of Assessment i+1) - (Date of Assessment i)]/2 \}$

Where Coeff i = 1 if Employment status equal to Employed or Temporarily Employed at Assessment i, Coeff i = 0 otherwise.

Treatment results will be compared using an independent groups t-test by means of the Satterthwaite method^[6]. The corresponding two-sided p-value will be presented. A two-sided p-value of <0.05 will be considered statistically significant. Mean difference, computed as colistimethate sodium - placebo, and corresponding 95% CI will also be presented.

The above summaries/analyses will be performed using the mITT Population.

Notes:

- [CCI] of first and last assessment will include only the subsequent period (referred to in the formula as part 2) and previous period (referred to in the formula as part 1), respectively.
- [CCI] relies on the assumption that no change [CCI] occurs during the [CCI] computed for each assessment.

4.7.6.8 [CCI]

The [CCI] will be provided overall and by treatment group. Percentages will be computed on the total number of subjects with at least one pulmonary exacerbation.

CONFIDENTIAL

Sponsor:	Zambon S.p.A.	Protocol Number:	Z7224L01
----------	---------------	------------------	----------

The relative risk of [CCI] for colistimethate sodium/placebo will be provided with 95% asymptotic CIs. Treatment differences will be assessed using a Fisher Exact test. A two-sided p-value of <0.05 will be considered statistically significant.

The number of [CCI] will be summarised presenting summary statistics for continuous variables on subjects with at least one [CCI].

Moreover, tables will present the number and percentages of subjects with at least [CCI] having:

- [CCI]
- [CCI]
- [CCI]
- [CCI]

The total duration of [CCI] will be summarised by treatment group using descriptive statistics for continuous variables.

The duration of [CCI] will also be reported for the following categorisations:

- [CCI] days;
- [CCI] days;
- [CCI] days;
- Not Evaluable.

In case of [CCI], the duration of [CCI] will be calculated using the following formula:

- Duration of [CCI] = [CCI] - [CCI] 1.

In case of missing [CCI] or [CCI] the [CCI] will be classified as "Not Evaluable".

The above summaries/analyses will be performed using the mITT Population.

4.7.6.9 [CCI]

For the [CCI] the score for the following domains will be calculated and analysed with a hierarchical approach as per the following order:

- [CCI] Domain: items 1, 2, 3, 4, 16;
- [CCI] Domain: items 17, 20, 25, 27, 28;
- [CCI] Domain: items 6, 8, 9;
- [CCI] Domain: items 7, 10, 11, 23;
- [CCI] Domain: items 18, 19, 22, 26;
- [CCI] Domain: items 12, 13, 14;

CONFIDENTIAL

Sponsor:	Zambon S.p.A.	Protocol Number:	Z7224L01
----------	---------------	------------------	----------

- CCI [REDACTED] Domain: items 5, 15, 21, 24;
- CCI [REDACTED] Domain: items 29, 30, 31, 32, 33, 34, 35, 36, 37.

Details for calculations are reported in [Appendix 2: CCI \[REDACTED\] Version 3.0](#).

The CCI [REDACTED] domain scores assessed at Visits 3 - 7 (End of Treatment) will be summarised by treatment group using descriptive statistics including 25th and 75th percentiles. Results for absolute changes from baseline will also be reported. Due to CTP amendments and to the corresponding changes in the procedures schedule, not all the subjects have undergone the same sequence of assessments. All the values collected will be summarised jointly. Considering the presence of a stratified and permuted blocks randomisation list no imbalance between treatments is expected.

Change from baseline in each CCI [REDACTED] domain score will be analysed using a linear mixed model for repeated measures including treatment, visit, treatment-by-visit interaction, use of stable concomitant therapy with oral macrolides and pooled site, i.e. country, as detailed in CCI [REDACTED] [REDACTED], as fixed effects and baseline value as covariate. An unstructured covariance matrix will be assumed and the Kenward-Roger adjustment will be used for the degrees of freedom. The least square means in each treatment group, the least square mean differences between treatments, their 95% CIs and associated p-values overall and at each visit will be estimated by the model. The OBSMARGINS option will be used. A two-sided p-value of <0.05 for the overall mean difference between treatments will be considered statistically significant.

The above summaries/analyses will be performed using the mITT Population.

